## PROTOCOL AMENDMENT SUMMARY OF CHANGES TABLE

Document History		
Document	Date of Issue	Type of Amendment
Amendment 5	27 Sep 2022	Substantial
Amendment 4	09 May 2022	Substantial
Amendment 3	03 Feb 2021	Substantial
Amendment 2	16 Dec 2019	Nonsubstantial
Amendment 1	06 Dec 2019	Nonsubstantial
Original Protocol	29 Oct 2019	Not applicable

This document cannot be used to support any marketing application and any extensions or variations thereof.  
PUBLIC COPY

**Amendment 5 (27 Sep 2022)****Overall rationale for the amendment**

Periodic worsening of HS symptoms is a well-known aspect of HS. This worsening has been described as “flaring” by both patients and physicians (Caposiena and Bianchi, 2020). However, there are several different definitions of flare, and no unanimous consensus has evolved over the course of the study on its meaning, including the flare definition used in previous and ongoing clinical studies (Kimball, 2016c and CT.gov citations for HS0003 and HS0004 studies). With no published validation studies, no information is available on the validity, repeatability, or sensitivity to change of any of the described definitions (Kirby 2020). Highlighting these points, inconsistent data on the flare endpoint have been observed within the bimekizumab program and in recently published data from another experimental HS treatment (Kimball, 2022). Given this information, which is external to and independent of any knowledge of the results of this study, the relevance of the flare endpoint as currently defined is questionable. For these reasons, the protocol is amended to remove the flare (secondary) endpoint from the statistical testing procedure. It will be included as an “Other” endpoint in the study.

Section # and Name	Description of Change	Brief Rationale
1.1 Synopsis 3 Objectives and endpoints	Removed flare from secondary objectives	To align with the overall rationale for the amendment
3 Objectives and endpoints	Added flare to “Other” objectives	
9.3.2 Analysis of secondary efficacy endpoints; Figure 9.1; Table 9.1	Removed flare from testing procedures	
References	Added references to support Protocol Amendment 5 overall rationale	
Throughout	Minor editorial and formatting revisions	Minor edits and formatting revisions that do not impact content were made for readability and/or clarity

## 1 PROTOCOL SUMMARY

### 1.1 Synopsis

**Protocol title:**

A Phase 3, Randomized, Double-blind, Placebo-Controlled, Multicenter Study Evaluating the Efficacy and Safety of Bimekizumab in Study Participants with Moderate to Severe Hidradenitis Suppurativa

**Short Title:**

A Phase 3, Randomized, Double-blind, Placebo-Controlled, Multicenter Study Evaluating the Efficacy and Safety of Bimekizumab in Study Participants with Moderate to Severe Hidradenitis Suppurativa

**Rationale:**

UCB is investigating bimekizumab (a humanized, full-length immunoglobulin [Ig] G1 monoclonal antibody [mAb] with high affinity for human interleukin [IL] 17 [IL-17A and IL 17F]) for the treatment of hidradenitis suppurativa (HS). Antibodies targeting IL-17A are effective in treating patients with moderate to severe psoriasis (PSO) and other immuno-inflammatory conditions. Data from clinical studies with bimekizumab suggest that inhibition of both IL-17A and IL-17F could be beneficial to patients with such conditions, including HS. Based on results from a Phase 2a study in study participants with HS (HS0001); and a Phase 2b study in study participants with PSO (PS0010) and its 48 week extension study (PS0011), bimekizumab doses of 320mg every 2 weeks (Q2W) in HS and 320mg every 4 weeks (Q4W) in PSO appeared to have an acceptable safety profile, and achieved clinically meaningful efficacy in both primary and key secondary endpoints in their respective studies. Based on these data and considering the high unmet need for safe and effective therapies for HS, confirmatory studies are being conducted with bimekizumab for the treatment of moderate to severe HS.

## Objectives and Endpoints

The primary and secondary objectives and associated endpoints are as follows:

Objectives	Endpoints
Primary	
Evaluate the efficacy of bimekizumab in study participants with moderate to severe HS	

• HiSCR50 at Week 16

Secondary	
Evaluate the efficacy of bimekizumab on other measures of disease activity in study participants with moderate to severe HS	

• HiSCR75 at Week 16

• Absolute change from Baseline in DLQI Total Score at Week 16

• Absolute change from Baseline in the Worst HS Skin Pain score at Week 16, as assessed by the “worst pain” item (11-point numeric rating scale) in the HSSDD

• Pain response (defined as a decrease from Baseline in HSSDD weekly worst skin pain score at or beyond the threshold for clinically meaningful change) at Week 16

Evaluate the safety of bimekizumab in study participants with moderate to severe HS	

• Treatment-emergent AEs

• Serious TEAEs

• TEAEs leading to withdrawal from study

AE=adverse event; AN=abscess and inflammatory nodule; DLQI=Dermatology Life Quality Index; HiSCR50=a 50% reduction in the total AN count with no increase from Baseline in abscess or draining tunnel count; HiSCR75=a 75% reduction in the total AN count with no increase from Baseline in abscess or draining tunnel count; HS= hidradenitis suppurativa; HSSDD=Hidradenitis Suppurativa Symptom Daily Diary; TEAE=treatment-emergent adverse event

## Overall Design

HS0003 is a Phase 3, randomized, double-blind, placebo-controlled, multicenter, pivotal study evaluating the efficacy and safety of bimekizumab in study participants with moderate to severe HS.

### Number of Participants

Approximately 490 study participants will be randomly assigned to study treatment: 140 for bimekizumab 320mg Q2W/Q2W, 140 for bimekizumab 320mg Q2W/Q4W, 140 for bimekizumab 320mg Q4W/Q4W, and 70 for placebo/320mg Q2W. The Randomized Set (ie, all randomized study participants) is the primary analysis set for efficacy analyses.

Screen failures are defined as participants who consent to participate in the clinical study but are not subsequently randomized to study treatment (Section 5.4).

## Treatment Groups and Duration

Study participants meeting the inclusion criteria who do not meet any exclusion criteria will complete a Screening Period of 14 days to up to 5 weeks; a double-blind, 48-week Treatment Period comprising a 16-week Initial Treatment Period and 32-week Maintenance Treatment Period; and a 20-week Safety Follow-up (SFU) Period following the final injection of investigational medicinal product (IMP) if study participants do not enter a subsequent extension study (HS0005) or withdraw prematurely from treatment. The total duration of study participation in HS0003 will be 68 to 71 weeks for those who complete HS0003 and do not participate in the extension study HS0005 and 50 to 53 weeks for those who participate in HS0005 and, thus, do not participate in the 20-week SFU Period.

Study participants will be randomized in a 2:2:2:1 ratio (stratified by Hurley Stage and current antibiotic use) to 1 of 3 dose regimens of bimekizumab or placebo as shown in the schematic (Figure 1-1). All doses of IMP will be administered by subcutaneous (sc) injection. The primary efficacy variable at Week 16 is HiSCR50 (a 50% reduction in the total AN count with no increase from Baseline in abscess or draining tunnel count). Study visits will occur at Screening; Baseline (Week 0); Weeks 1, 2, 4, 6, 8, 10, 12, 14, and 16; every 2 weeks from Week 16 through Week 48 for assessments of efficacy, safety, and other measures of quality of life/health status/work productivity; and a SFU visit 20 weeks after the last dose of IMP for participants who do not enter the extension study.

An independent Data Monitoring Committee (DMC) will periodically review unblinded efficacy and safety data to assess the benefit/risk of bimekizumab in study participants with moderate to severe HS.

[REDACTED]

[REDACTED]

[figure not shown]
[REDACTED]

[REDACTED]

## 1.2 Schema

A schematic diagram for the study is presented in [Figure 1-1](#).

**Figure 1-1: Study Schematic**

HiSCR50=a 50% reduction in the total abscess and inflammatory nodule count with no increase from Baseline in abscess or draining tunnel count;

IMP=investigational medicinal product; Q2W=every 2 weeks; Q4W=every 4 weeks

\*Week 16 = primary endpoint (HiSCR50 bimekizumab versus placebo)

a Study participants should discontinue from the study from Week 32 on if no partial response is achieved (partial response is defined as  $\geq 25\%$  improvement in abscess and inflammatory nodule count relative to Baseline [Week 0] lesion values.)

b Study participants achieving an improvement of at least 25 % in abscess and inflammatory nodule count continue in HS0005 (Extension Study).

c 20-week Safety Follow-up (from last IMP injection) for any study participant who discontinues from study prior to Week 48, or who does not continue in HS0005.

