### 3 OBJECTIVES AND ENDPOINTS

Objectives	Endpoints
Primary	
Evaluate the efficacy of bimekizumab in study participants with moderate to severe HS	

• HiSCR50 at Week 16

Secondary	
Evaluate the efficacy of bimekizumab on other measures of disease activity in study participants with moderate to severe HS	

• HiSCR75 at Week 16

• Absolute change from Baseline in DLQI Total Score at Week 16

• Absolute change from Baseline in Skin Pain score at Week 16, as assessed by the “worst pain” item (11-point numeric rating scale) in the HSSDD

• Pain response (defined as a decrease from Baseline in HSSDD weekly worst skin pain score at or beyond the threshold for clinically meaningful change) at Week 16

Evaluate the safety of bimekizumab in study participants with moderate to severe HS	

• Treatment-emergent AEs

• Serious TEAEs

• TEAEs leading to withdrawal from study

Other	
Evaluate the efficacy of bimekizumab on HiSCR, other HS Scores, and other clinical measures of disease activity at various timepoints in study participants with moderate to severe HS	

• Time to response of HiSCR25, HiSCR50, HiSCR75, HiSCR90, and HiSCR100

• HiSCR25, HiSCR50, HiSCR75, HiSCR90, and HiSCR100

• Absolute change from Baseline in International Hidradenitis Suppurativa Severity Score System

• Change from Baseline in the HS-Physician’s Global Assessment 6-point scale

• Absolute and percentage change from Baseline in hs-CRP

• Initiation of systemic antibiotic rescue therapy

• HiSCR25, HiSCR50, HiSCR75, HiSCR90, and HiSCR100 at both Weeks 16 and 48

• Time to loss of response of HiSCR50, HiSCR75, HiSCR90, and HiSCR100 in Week 16 responders

• Partial responders (defined as a <math>\geq 25\%</math> reduction in AN count from Baseline [Week 0]) at Week 16 who progress to HiSCR50 during the Maintenance Treatment Period

Objectives	Endpoints

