The Maintenance Treatment Period is designed to assess the durability of response of the study endpoints and to provide sufficient longer-term (up to 48 weeks, including the Initial Treatment Period) safety and exposure to bimekizumab for regulatory filings. Continuous (up to 48 weeks) exposure to both the 320mg bimekizumab Q2W and 320mg bimekizumab Q4W dose regimens allow for the following assessments:

- Durability of response and longer-term safety
- Optimal dosing interval for maintenance treatment

This period will also allow study participants who received placebo in the Initial Treatment Period to begin receiving bimekizumab at Week 16 in the randomized, controlled Maintenance Treatment Period of the study.

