## **6.8 Treatment after the end of the study**

Study participants who complete HS0003 will have the option of enrolling in a Phase 3, multicenter, extension study (HS0005).

Study participants who elect not to enroll in HS0005 at Week 48 will be scheduled to have the SFU Visit 20 weeks after the final injection of IMP. During the SFU, if study participants' HS deteriorates, the Investigator may consider standard of care for HS treatment after discussion with the Medical Monitor or UCB study physician. Note that the half-life of bimekizumab must be considered in selection of appropriate HS treatments during the SFU period. All concomitant

medications and HS interventions administered during the SFU will be recorded on the appropriate eCRF pages.

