## **7 DISCONTINUATION OF STUDY MEDICATION AND PARTICIPANT DISCONTINUATION/WITHDRAWAL**

### **7.1 Discontinuation of study medication**

Study medication will be stopped if the study participant develops a medical condition, adverse event (AE), or laboratory abnormality that, in the opinion of the Investigator, compromises the safety of the study participant or his or her ability to continue participation in the study. Study participants who are discontinued from IMP should be encouraged by the Investigator to return for all scheduled visits through Week 48, and the SFU Visit (if the Week 48 Visit is  $\geq 20$  weeks after the final dose of IMP, the SFU Visit is not required). Any study participant who discontinues IMP but continues in the study should be discussed with the Medical Monitor or UCB study physician.

In all cases the study participant should be followed until the condition has resolved as agreed by the Investigator and the UCB study physician. Investigators should contact the Medical Monitor and/or UCB study physician, in advance whenever possible, to discuss the withdrawal of a study participant.

Study medication will be stopped if the study participant has a confirmed positive coronavirus disease 2019 (COVID-19) test result or a suspected COVID-19 infection. Study medication can be resumed after the participant's recovery from COVID-19, based on the Investigator's clinical judgement. All such cases must be discussed with the Medical Monitor or UCB study physician.

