#### **7.1.1 Study participant does not achieve partial response**

If a study participant does not achieve a partial response (defined as a  $\geq 25\%$  reduction in AN count from Baseline [Week 0]) at any visit from Week 32 to 46, the Investigator should contact the Medical Monitor to discuss whether the study participant should continue on study.

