## 7.2 Participant discontinuation/withdrawal from the study

Note: For female study participants, please see Section 8.3.5 for pregnancy that occurs during the study as evidenced by a positive pregnancy test.

Study participants are free to withdraw from the study at any time, without prejudice to their continued care.

A study participant may withdraw from the study at any time at his or her own request, or may be withdrawn at any time at the discretion of the Investigator for safety, behavioral, compliance, or administrative reasons.

If the study participant withdraws consent for disclosure of future information, the Sponsor may retain and continue to use any data collected before such a withdrawal of consent.

If a study participant withdraws from the study, he or she may request destruction of any samples taken and not tested, and the Investigator must document this in the site study records.

See the Schedule of Activities (Table 1-1) for data to be collected at the time of study discontinuation and follow-up and for any further evaluations that need to be completed.

If a study participant does not achieve a partial response (defined as a  $\geq 25\%$  reduction in AN count from Baseline [Week 0]) at any visit from Week 32 to 46, the Investigator should contact the Medical Monitor to discuss whether the study participant should continue on study.

Study participants will be withdrawn from the study, after being encouraged to complete the Premature End of Treatment (PEOT) and the SFU Visit if either of the following events occur:

1. Study participant withdraws his or her consent.
2. The Sponsor or a regulatory agency requests withdrawal of the study participant.

Study participants should be withdrawn from IMP and encouraged by the Investigator to return for all scheduled visits through Week 48, and the SFU Visit (if the Week 48 Visit is  $\geq 20$  weeks after the final dose of IMP, the SFU Visit is not required) if any of the following events occur:

1. Study participant develops an illness that would interfere with his or her continued participation.
2. Study participant is noncompliant with the study procedures or medications in the opinion of the Investigator.

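### Figure 1-1 footnote a sends participants without a partial response out of the study from Week 32, while Sections 7.1.1 and 7.2 ask only for a Medical Monitor discussion (minor)

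*Protocol*

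**What the plan says.** The schematic in Section 1.2 carries a rule for participants whose AN count has not fallen by at least 25% from Baseline. Figure 1-1 footnote a reads: "Study participants should discontinue from the study from Week 32 on if no partial response is achieved".

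Section 7.1.1 covers the same participant, with the same threshold, over visits from Week 32 to Week 46. There "the Investigator should contact the Medical Monitor to discuss whether the study participant should continue on study". Section 7.2 repeats this in a paragraph of its own.

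Two other provisions bear on what follows:

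- Section 7.1, the parent of 7.1.1, deals with stopping study drug: "Study participants who are discontinued from IMP should be encouraged by the Investigator to return for all scheduled visits through Week 48".
- Section 7.2 has a short list of events that end study participation, introduced by "Study participants will be withdrawn from the study, after being encouraged to complete the Premature End of Treatment (PEOT) and the SFU Visit". It then has a longer list of events that end dosing. Lack of partial response is in neither list.

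Section 4.2 says what the Maintenance Treatment Period is for. Besides durability of response and longer-term safety, it names "Optimal dosing interval for maintenance treatment". Section 3 lists, among the Other endpoints, HiSCR response "at both Weeks 16 and 48", time to loss of response, and flare by Week 48.

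**The concern.** A participant below the threshold at Week 32 meets two instructions in current protocol text. Under footnote a the default is to leave. Under Sections 7.1.1 and 7.2 the default is a conversation, after which the participant may stay on drug and keep being assessed.

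The difference affects the data. Leaving the study because of a low response removes later lesion counts from the people who respond worst, so the missingness depends on outcome. If one maintenance regimen is weaker, it would also fall unevenly between regimens. A statistical analysis plan can say how missing Week 48 counts are analysed. It cannot recover counts that were never taken, and it cannot decide which withdrawal rule the sites apply.

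**Working it through.** The point rests on no sample size, power or alpha figure, so the check is a comparison of texts plus one count from the dosing schedule.

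**1. Same population?** Yes. Footnote a, Section 7.1.1, Section 7.2 and the definition in Section 8.1.2 all use a 25% AN reduction from Baseline, and the window opens at Week 32 in each of the first three.

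**2. Same action?** No.

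| Text | Default for a participant below 25% |
|---|---|
| Figure 1-1 footnote a | Should leave the study |
| Section 7.1.1 | Investigator and Medical Monitor discuss whether to continue |
| Section 7.2, own paragraph | As 7.1.1 |
| Section 7.2, events ending study participation (2 items) | Not listed |
| Section 7.2, events ending dosing (10 items) | Not listed |

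**3. Is either text superseded?** No. Footnote a is part of the current schema, not of the amendment history, and no section ranks one text above the other.

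**4. What differs downstream?** Section 7.2 gives a participant who leaves, and does not attend the remaining visits, a Premature End of Treatment visit and a Safety Follow-up visit. Section 7.1 asks a participant who only stops drug to keep attending through Week 48. The first route ends the scheduled lesion counts; the second aims to keep them.

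**5. How much of the schedule is involved?** Section 6.1 and Table 6-2 give dosing every 2 weeks from Week 0 to Week 46.

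- All dosing visits: (46 − 0)/2 + 1 = 24.
- Dosing visits from Week 32 to Week 46: (46 − 32)/2 + 1 = 8.

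A participant who leaves at Week 32 before dosing therefore forgoes 8 of 24 dosing visits, and the Week 48 lesion count.

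**6. What is not involved?** Section 9.8 places the primary and secondary comparisons at Week 16. Section 9.2 limits formal testing to those variables and treats p-values for other endpoints as nominal. The earliest action under either text is at Week 32, so nothing in the testing procedure of Section 9.3.2 or in Table 9-1 changes.

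**7. Can the number affected be computed?** No. The protocol gives no expected share of participants below 25% from Week 32 on.

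**The case against.** The strongest reply is that Section 7.1 and Section 7.2 both ask Investigators to contact the Medical Monitor, in advance whenever possible, before a withdrawal. A site that follows footnote a should therefore make the same call that Section 7.1.1 requires. The body rule also appears twice, in the sections that govern discontinuation, whereas the footnote is a single line under a schematic. This stands, and it removes most of the worry about withdrawal varying freely between sites. It does not remove the conflict: in one text the call precedes an expected exit, in the other it decides an open question.

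A reader might infer three stronger points.

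- **The Week 48 regimen comparison is biased by a known amount.** The documents do not support this. Take assumed inputs: 10% and 20% of counts below threshold in two regimens, true Week 48 response of 60% and 50%, and within-participant correlation of 0.5 to 0.8 on a latent normal scale. If everyone with any of four counts below 25% leaves, the true 10-point contrast appears as about 1 to 3 points among those observed. If only those with all four counts below leave, it appears as about 7.5 to 9 points. The answer is set by the assumptions and by the reading of the rule. The protocol states no observed-only Week 48 analysis and no formal regimen comparison.
- **The trigger must be redefined as one or more low counts.** The wording in Section 7.1.1 can be read as one low count or as no adequate count. But the trigger only starts a discussion, and choosing a stricter one is a design decision, not a correction.
- **Entry to the extension study is contradictory.** Footnote b says "Study participants achieving an improvement of at least 25 % in abscess and inflammatory nodule count continue in HS0005", while Section 6.8 says "Study participants who complete HS0003 will have the option of enrolling in a Phase 3, multicenter, extension study (HS0005". An option to enrol does not exclude eligibility conditions, and that study's criteria are not shown.

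**Conclusion.** The conflict is real, sits in current text and is minor. Footnote a directs exit where Sections 7.1.1 and 7.2 leave the decision to the Investigator and the Medical Monitor. It is slightly more than clerical, because the directive would end lesion counts on account of poor response, in the period meant to show durability and inform maintenance dosing.

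The reach is limited to Maintenance Period endpoints classed as Other and to safety and exposure data after Week 32. For one participant leaving at Week 32, that is up to 8 of 24 dosing visits and the Week 48 count. The number of such participants is unknown. That losses would concentrate in a weaker regimen is an assumption, since the protocol gives no response rates for that period.

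**What to change.** - **Figure 1-1 footnote a:** replace the directive with a pointer, for example: *For participants without a partial response from Week 32 on, see Section 7.1.1.* This alone resolves the conflict.
- **Sections 7.1.1 and 7.2:** add one sentence saying that participants who stop study drug for this reason are encouraged to attend all scheduled visits through Week 48, as Section 7.1 already provides.

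The cost is one footnote and one repeated sentence. No assessment is added, the Medical Monitor's role and the threshold stay as they are, and blinding is unaffected.

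The benefit depends on timing. Section 9.8 says randomization was complete before the pain-response endpoint was added, and the amendment history dates that addition to Amendment 4 on 09 May 2022. Amendment 5 followed on 27 Sep 2022, 141 days (141/7, about 20 weeks) later. Everyone still in the study was by then at least about 20 weeks past randomization, so the change can help only those not yet at Week 48. For withdrawals that have already occurred, the study report can state which rule was applied.
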